Analyses: Torque characteristics including mean, peak, and integrated torque, torque duration, and torque derivation of voluntary and electrical stimulation attempts will be calculated using customized Labview (National Instruments, Austin, TX) software. Efficacy in voluntary movement will be measured by calculating peak force relative to stimulation amplitude. Task specific leg muscle electromyography outcomes (amplitude, duration, and onset and offset) appropriate for the movements will also be used to assess quality of movement. Electromyography data will be full wave rectified and filtered using a 4th order bandpass Butterworth filter (40Hz - 500 Hz) representing the relative number and frequencies of the motor units recruited per burst. Integrated electromyography will assess the total electromyography activity generated during specific phases of the motor tasks.

2. Cardiovascular.

a. Ambulatory BP and Heart Rate monitoring.

Procedure: Twenty-four hour ECG will be performed using Edan 3-channel Holter with continuous heart rate monitoring. Twenty-four-hour ABPM will be performed using the ABPM-05 (Meditech) monitor. The device will be fixed with appropriate cuff sizes to the non-dominant arm and pre-programmed such that systolic blood pressure (SBP), diastolic blood pressure (DBP), and heart rate (HR) will be recorded automatically every 15 minutes during their daytime active period, then hourly overnight. For participants who have a scheduled bowel routine within the 24-hour monitoring period, recordings at 5-minute intervals for 30 minutes before, during, and for 30 minutes after the routine will be programmed. Additionally, participants will be instructed to initiate a self-measurement any time they experience symptoms of or completed an activity that may trigger a hypo- or

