hypertensive episode. Testers will provide examples of such symptoms/episodes. Additionally, the subject diary will include examples of activities that may result in hypo- or hypertensive events and instructions on how to take a self-measurement in this instance. Participants will be asked to write down notes regarding blood pressure related symptoms, activities and their time-points, and the time they wake-up and fall asleep in a participant diary. In the case of tetraplegic individuals with impaired hand function, caregivers/nurses will be asked to provide notes in the diary. Participants will be given both verbal and written instructions for wearing the device to ensure blood pressure measurements are taken accurately.

Analysis: Twenty-four-hour ambulatory blood pressure monitoring data will be stored and analyzed upon completion of the assessment [108, 109]. The EasyABPM 1.1.1.2 software package (Meditech) provides several report files once the data is loaded onto the computer from the device monitor. Baseline SBP and DBP will be established by calculating the average of 3 consecutive resting blood pressures while seated in the morning. Baseline blood pressure will be used to assess the number of hypertensive and hypotensive events during the daytime [6, 12, 110-113]. The blood pressure and heart rate data will be divided into four time period groups: Total 24 hour Period, Active Period (awake), Passive Period (asleep), and Special Event Period (morning routine or bowel program). Each time period group will be further separated into three data parameters: systolic blood pressure, diastolic blood pressure, and heart rate. Histograms will be created demonstrating the mean percentage of time each data parameter falls within a specific data range during the allotted time period. Blood pressure will be separated into data ranges of 10 mmHg. Heart rate will be separated into data ranges of 10 beats per minute.

b. Orthostatic Stress Test

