Procedure: Participants will participate in laboratory sessions until all optimal configurations for joint movement and trunk control are found. Participant will demonstrate safe use of the patient programmer and ability to perform the leg voluntary movement independently or in the presence of a care giver. This will take approximately 3–5 days. Once the participant has demonstrated safe use of programs they will be allowed to conduct the sessions at home. Participants will be asked to train daily (7 days a week) for a total of 80 sessions.

Participants in the Voluntary-scES group (A1) will receive Core voluntary training focusing on trunk exercises, sitting balance, and lower extremity training for 6 hours daily. Voluntary training will be performed in the laboratory under supervision of trained research staff until they can perform each task safely and independently. Then they will be able to conduct their training at home. Approximately every two weeks, lower extremity voluntary configurations will be assessed by research staff to make sure they are still optimized for the desired movement. They may train in the laboratory more often.

3. Cardiovascular Intervention.

Participants will undergo testing in the laboratory to determine the optimal stimulator configuration(s) for blood pressure regulation. The first 5 training sessions will be performed in the laboratory. Once 3 consecutive stable days are achieved with the same stimulation parameters and the participant has demonstrated safe use

of the programmer, they will be sent home for one day to perform the stimulation at home. The participant will return to the laboratory the following day for stimulation with blood pressure monitoring. Provided cardiovascular parameters remain stable, the participant will be allowed to train at home for 3 days prior to returning to the laboratory for stimulation with monitoring. If cardiovascular parameters remain stable, the participant will be able to begin the home training program of 6 days a week and 1 day in lab training. Participants will be asked to train with CV-scES for CV for approximately 6 hours daily (7 days a week) for a total of 80 CV training sessions. Participants are instructed to monitor blood pressure for at least 15 minutes prior to starting CV-scES each day in order to insure a stable baseline prior to starting stimulation.

4. Stand Intervention.

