- Significant changes in heart rate and/or blood pressure
- Muscle and joint soreness

Rare

- Chest pain
- Joint sprain or muscle strain
- Fall
- Broken bones requiring medical treatment
- Broken bones requiring surgical treatment and long-term medical follow-up

Risks of Cardiovascular Training Intervention

Less Likely

- Shortness of breath
- Significant changes in heart rate and/or blood pressure

C. Adequacy of Protection against Risk

1. Recruitment and Informed Consent: Recruitment of patients will be performed through our secure research database that includes over 5,000 individuals registered with SCI. All potentially eligible research participants will be invited to Frazier Rehab Institute to discuss the complete protocol, including risks and benefits with [name] and/or designated research staff. The informed consents will be written in language that an eighth-grade student would be able to understand and will contain information on all studies to be performed as well as contact information if the subject and his/her associates should have any questions. All potential research participants will be encouraged to read the pre-screening, screening, and surgical interventions informed consent(s) and discuss the study with their physician, family and friends, before signing each of the three IRB approved informed consents. The original signed informed consents will be kept in a locked cabinet in a locked room within an area of controlled access. A scanned copy will be stored on our server with password protection. Eligibility checklists will be signed by [name] with all source documentation and stored in a locked cabinet in a locked room within an area of controlled access. A scanned copy will be stored on our server with password protection.

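### Ambulatory blood pressure is not split by stimulator state, so stimulated and unstimulated awake hours are pooled: readings are diluted and cannot be attributed to stimulation

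*Protocol*

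**What the plan says.** **Windows and summaries.** Section III.D.2.a has the ambulatory data "divided into four time period groups: Total 24 hour Period, Active Period (awake), Passive Period (asleep), and Special Event Period". The special-event window covers the morning or bowel routine. Two summaries are planned. The first is a distribution: "Histograms will be created demonstrating the mean percentage of time each data parameter falls within a specific data range during the allotted time period", with blood pressure in bands of 10 mmHg. The second is a count: "Baseline blood pressure will be used to assess the number of hypertensive and hypotensive events during the daytime".

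**Sampling and diary.** Pressure is "recorded automatically every 15 minutes during their daytime active period, then hourly overnight", with extra readings around a bowel routine and self-measurements when symptoms occur. The diary asks for symptoms, timed activities, and waking and sleeping times. It does not name stimulator start or stop.

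**Exposure.** Section III.E.3 states: "Participants will be asked to train with CV-scES for CV for approximately 6 hours daily (7 days a week". After a stepwise release, "the participant will be able to begin the home training program of 6 days a week and 1 day in lab training". The pressure check it sets on home days comes before stimulation: "Participants are instructed to monitor blood pressure for at least 15 minutes prior to starting CV-scES each day". Section IV.B lists "Significant changes in heart rate and/or blood pressure" among the risks of the cardiovascular training.

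**Schedule.** In Appendix #1 the orthostatic stress test, vascular ultrasound, echocardiography and pulse wave velocity carry the symbol for testing with and without stimulation at every time point after implantation. The ambulatory pressure and heart rate rows carry a plain X at Screen, Pre-Usual Care, periodically and monthly during the interventions, after each intervention, and at follow-up. They have no X at Pre-implant.

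**The concern.** The protocol's own pilot record suggests that the two states differ. The Figure 2 legend reports that one participant's pressure fell when stimulation was switched off and recovered when it was switched on again. The Rationale (II.B) makes a separate claim, that cardiovascular gains lasted through the day without stimulation. These are different effects. The ambulatory recording is the scheduled outcome that observes daily life and can cover a whole home session.

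Without a split by state, three things are lost. The share of high or low readings during stimulation is reduced by the unstimulated hours in the same window. A hypertensive or hypotensive event cannot be assigned to stimulation or to its absence. A change from the pre-surgery recording, which contains no stimulated hours, cannot be read as either an effect present only during stimulation or a lasting one.

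**Working it through.** No figure in the protocol bears directly on this point, so there is none to reproduce. The check is arithmetic on shares.

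**Inputs**
- Stimulated time: about 6 hours a day (III.E.3).
- Sampling: 4 readings an hour awake, 1 an hour overnight (III.D.2.a). Extra bowel-routine and self-initiated readings are ignored.
- Awake time: not given. Assumed 16 hours, range 14–18.
- Assumed: the participant trains on the monitoring day, with all stimulation while awake.

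**1. Stimulated share of each window**
- Awake: f = 6 / awake hours. 6/14 = 0.43, 6/16 = 0.375, 6/18 = 0.33.
- 24 hours by time: 6/24 = 0.25.
- Readings on stimulation: 6 × 4 = 24, out of 56, 64 or 72 awake readings. Off stimulation, awake: 32, 40 or 48.
- 24 hours by readings: 24/(56+10) = 0.36, 24/(64+8) = 0.33, 24/(72+6) = 0.31.

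**2. Dilution in the awake histogram**
Pooled share = f × p_on + (1 − f) × p_off. Take p_on = 50% and p_off = 0% for illustration:
- 14 hours awake: 0.429 × 50% = 21.4%
- 16 hours awake: 0.375 × 50% = 18.8%
- 18 hours awake: 0.333 × 50% = 16.7%

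The range is 17–21%.

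**3. On-only or lasting?**
Suppose that 50% of awake readings are low before surgery, with 16 hours awake (illustrative).
- On-only effect: 0% low on stimulation, still 50% off. Pooled: 0.625 × 50% = 31.25%.
- Lasting effect: 31.25% low in both states. Pooled: 31.25%.

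The pooled share of low readings is identical, although in the first case nothing has changed off stimulation.

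**4. Do high and low readings cancel?**
Only if each window were reduced to a mean. With 16 hours awake, a 20 mmHg rise on stimulation moves the awake mean by 0.375 × 20 = 7.5 mmHg, and a 12 mmHg fall off stimulation moves it back by 0.625 × 12 = 7.5 mmHg. Section III.D.2.a does not specify that mean. In its bands, the readings stay apart. For example, assume normal distributions with mean systolic pressure 145 mmHg on and 95 mmHg off, SD 12 and a cut of 140. Then 66% of stimulated time is at or above the cut, and the pooled awake figure is 25%. About 16 of the 24 stimulated readings remain visible in the high bands. That is dilution, not cancellation.

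**5. Arms and periods**
Table 1 adds 2 hours of stand stimulation in Group B and, in the second period, for everyone. If these hours come on top of the 6, the stimulated share on a stand-training day is 8/18 to 8/14, or 44–57%. The mixture then varies by arm, by period and by day, because stand training runs 5 days a week (III.E.4).

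**The case against.** **Cancellation.** A reader might infer that high pressure during stimulation is offset by low pressure off it, so that the day looks normal. The documents do not support this. The planned summaries are percentages of time in 10 mmHg bands plus counts of hypertensive and hypotensive events. A participant high on stimulation and low off it would show two clusters, not a normal day. Event counts are not diluted at all.

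**Whole-day pressure is a legitimate target.** The Rationale aims at stable blood pressure in daily living, so pooled windows answer a real question. This stands, and the pooled windows should stay. The split answers a further question.

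**Stimulator state is studied elsewhere.** Four other cardiovascular tests are scheduled in both states. This stands and confines the gap to one test, but those are laboratory sessions and do not describe daily life.

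**Safety.** A reader might also infer that home stimulation goes unsupervised. It does not: III.E.3 requires initial laboratory sessions, stable days before release, monitored returns and a weekly laboratory day. Section IV.C.2.b limits home programs to those tested in the laboratory and tells participants to call about complications. The histogram is not the safety control.

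**Stimulation on monitoring days is inferred.** The protocol does not state it; it follows from daily training and the intervention-phase columns. At follow-up it is untrue of anyone whose stimulator has been removed. The point is therefore conditional.

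**The analysis plan could add the split.** It could, and timed activities in the diary may catch some sessions. But the protocol itself fixes the windows and the diary items, and a later plan cannot reliably recover switching times that nobody was asked to write down.

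**Conclusion.** The point holds as one of pooling, dilution and lost attribution in the ambulatory outcome. With training as scheduled on monitoring days and 14–18 waking hours, 33–43% of awake time is stimulated. When off-time contributes no high readings, the awake histogram shows only that fraction of the on-stimulation share. Event counts are intact but unattributed, and on-only and lasting effects can give the same pooled result. The pressures and reading shares above are illustrations, not predictions.

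It does not follow that the outcome measures the wrong exposure, that harm is hidden, or that every recording after implantation is a mixture. This is a worthwhile, inexpensive improvement to one test, best made before diaries are issued.

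**What to change.** 1. In the ambulatory monitoring diary, add stimulator start and stop times and the type of stimulation (voluntary, cardiovascular or stand).
2. Keep the four existing windows. Add stimulation-on and stimulation-off subdivisions of the Active Period.
3. For each state, report the planned 10 mmHg bands and the hypertensive and hypotensive event counts, the counts per hour or per reading because the two states differ in length.
4. For lasting recovery, compare off-stimulation readings with the Screen or Pre-Usual Care recording, and name which. None is scheduled at Pre-implant, and both available recordings precede at least 80 days of usual care.

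Treatment does not change. The cost is one diary item and one grouping variable. About 24 readings per 6-hour session make the on-state estimate less precise than the pooled one. On and off hours also differ in posture, activity and time of day, since cardiovascular stimulation is given sitting or supine. The on-off comparison, and that of selected off hours with a full-day baseline, should be labelled descriptive.

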Procedure: The orthostatic stress test is utilized to assess orthostatic tolerance, to diagnose orthostatic hypotension, evaluate baroreflex responses, and assess beat-to-beat blood pressure and heart rate variability in individuals with SCI [114, 115]. Each participant will be assessed in the morning in a quiet, temperature-controlled (~72°F/22°C) laboratory at the Kentucky Spinal Cord Injury Research Center. Their diet will be restricted to exclude caffeine, alcohol, and foods that are high in fat the evening prior and the morning before the study. Participants will be asked to void their bladder right before arriving and to have completed their bowel program in advance if possible.

Participants will be placed in a cardiac chair (Chair Hydraulics, Steris Corp., Mentor, OH) or on a tilt-table (Hausmann Wheelchair Accessible Hi-Lo Tilt-Table, Patterson Medical, IL). Before the recording begins, each participant will be acquainted with the equipment and study setup. Continuous beat-to-beat arterial blood pressure will be recorded from a cuff placed around the finger using a Finapres Medical Systems unit. Brachial arterial blood pressure measurements will be taken periodically with a Dinamap V100 (GE Medical Systems) device for calibration and as a reference. A 3-lead or 12-lead ECG (ML132, AD Instruments) will be placed for electrocardiographic monitoring. Respiratory kinematics (chest and abdominal wall movements) will be acquired using two belt transducers (AD Instruments). Participants will rest in the supine position to allow for relaxation after the preparatory period. Next, baseline values will be recorded in the supine position. Then participants will be passively moved into the upright seated position in the cardiac chair or into the head up position on the tilt table (20-90 degrees) (Wecht et al. 2009, Wecht et al. 2003). While the participant is seated or tilted, we will record cerebral blood flow by transcranial Doppler, ultrasound of the heart and vessels, and pulse wave velocity (all of which are described in this protocol and previously approved) in addition to the standard beat-to-beat blood pressure and heart rate. The assessment will be stopped if: the participants experience symptoms of Orthostatic Intolerance, if high blood pressure persists without normalizing, or if the participant requests to be returned to the supine position.

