While the participant is supine, seated, or head up tilted the Orthostatic Intolerance Questionnaire will be administered periodically to determine if the participant is experiencing symptoms of orthostatic intolerance. The Orthostatic Intolerance Questionnaire is a 0-10 scale (0= no symptom and 10= intolerable) questionnaire that ranks the following symptoms: headaches, dizziness, blurred vision, nausea, weakness, confusion, fatigue, ringing of ears, and passing out. Symptom severity, or lack thereof, while upright will be compared to the participant's symptoms in the supine position.

During the orthostatic stress test, there may also be blood drawn to measure plasma catecholamines. In this case, prior to beginning the study, a butterfly catheter will be inserted into an antecubital vein to allow for the collection of blood samples at the different time points. Eight milliliters of venous blood will be drawn from an antecubital vein at the end of the supine phase to assess baseline epinephrine and norepinephrine levels. In the seated or head up tilted position, to assess the catecholamine responses to orthostatic stress, blood will

be drawn at minutes 3, 10, and at the end of the upright or tilted period. If the participant experiences symptoms of orthostatic intolerance or requests to end the seated/tilted position early, blood will be drawn immediately upon return to the supine position.

In individuals with the implanted stimulator, cardiovascular parameters at rest and in response to orthostatic challenge (sit up or tilt table positioning) may also be examined during stimulation, with optimal stimulation parameters determined previously using an established protocol.

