Analysis: Beat-to-beat systolic blood pressure, diastolic blood pressure, heart rate, and R-R intervals will be calculated from continuous blood pressure recordings and electrocardiography throughout the supine and upright/tilted periods. During the sit-up and head-up tilt, mean blood pressure and heart rate will be analyzed in 1-minute intervals during the supine and upright positions. During head-up tilt, continuous blood pressure will be analyzed to determine the percentage of systolic blood pressure beats that fall below 110 mmHg, as well as the percentage of beats that are decreased from average supine systolic blood pressure by 10 mmHg or more. Spectral power values and baroreflex variables will be calculated during the supine rest phase (see below). For sit-up and head-up tilt positions, spectral power / baroreflex variables will be analyzed during the 5-minute window that includes around the lowest 1-min systolic blood pressure interval; these outcomes may also be analyzed during the position change on the tilt table. We will also track the time duration of the head up tilt position as an outcome measure of orthostatic tolerance.

Autonomic balance will be assessed by spectral power density, based on Welch's modified periodogram technique. Beat-to-beat variables will be interpolated with a 5 Hz sampling rate by using a cubic spline, and then detrended with a straight line fitted to the data series. Power spectral density estimates will be made from 1-minute windows with 50% overlap. 512 points will be used in FFT. Spectral power will be calculated for low (LF, 0.04-0.15 Hz) and high (HF, 0.15-0.4 Hz) frequency regions by integrating the power spectral density curve by using trapezoidal integration.

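### Head-up tilt duration serves as a measure of orthostatic tolerance, although a tilt may also end for persistent high blood pressure or on request

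*Protocol*

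**What the plan says.** Protocol section III.D.2.b, Orthostatic Stress Test, gives three reasons for ending the test in its Procedure text. The first is symptoms: "The assessment will be stopped if: the participants experience symptoms of Orthostatic Intolerance". The second is "if high blood pressure persists without normalizing". The third is "or if the participant requests to be returned to the supine position".

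The Analysis text of the same section then sets the outcome: "We will also track the time duration of the head up tilt position as an outcome measure of orthostatic tolerance". No reason for stopping is attached to that duration.

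The section itself separates symptoms from requests. For the catecholamine samples it provides for an early draw with the words "If the participant experiences symptoms of orthostatic intolerance or requests to end the seated/tilted position early". No planned tilt length is given. The samples are to "be drawn at minutes 3, 10, and at the end of the upright or tilted period", and that end is not fixed. The tilt angle may lie anywhere from 20 to 90 degrees.

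Appendix #1 schedules the test at screening, before usual care and before implant without stimulation. From the post-implant visit onward it is marked as done with and without stimulation.

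**The concern.** Of the three stop reasons, only symptoms are orthostatic intolerance by definition. A request may or may not reflect it. Persistent high pressure is the opposite response to the one that a tolerance measure is meant to detect. With unqualified duration, a tilt ended at a given minute for high pressure and one ended at the same minute for presyncope receive the same value.

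High-pressure stops are plausible in this population. Inclusion criterion 7 (section IV.A) admits participants on the basis of autonomic dysreflexia symptoms or highly variable pressures, and section IV.C.2.b plans for dysreflexia and sustained pressure elevation under stimulation. They may also differ by condition. The Rationale (section II.B, cerebrovascular function) expects CV-scES to raise blood pressure. Tilts before implant cannot include a stimulation-induced high-pressure stop, whereas later stimulated tilts can. At stake is whether the tilt-duration result can be read as orthostatic tolerance when stimulated tests are compared with baseline or with unstimulated tests.

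**Working it through.** The protocol gives no tilt length, stop rate, variance or effect size for this outcome, so there is no figure to reproduce.

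**Step 1: the definition.** Duration runs from the start of tilt to whichever comes first: symptoms, high pressure, request or the end of the test. Only the first, and requests made because of symptoms, measure intolerance. The outcome is therefore an all-cause time under a cause-specific name.

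**Step 2: direction, by illustration.** Every input from here on is an assumption. Take a tilt of at most T minutes, constant hazards h1 (symptom stops) and h2 (high-pressure stops), and no stops on request. If a risk p is the probability of that stop by T in the absence of the other, then h = -ln(1-p)/T. Mean tilt time is (1-exp(-hT))/h, with h = h1 for symptom stops only and h = h1+h2 when any stop ends the time.

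With T = 30:

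| Symptom-stop risk | Symptom stops only | Any stop, high-pressure risk 5% | 15% | 30% |
|---|---|---|---|---|
| 60% | 19.6 min | 19.2 | 18.4 | 17.0 |
| 30% | 25.2 min | 24.6 | 23.4 | 21.4 |

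Worked entry: h1 = -ln(0.4)/30 = 0.03054, so the mean is 0.6/0.03054 = 19.6 minutes. The reduction is about 2% at a 5% risk (19.6 to 19.2; 25.2 to 24.6) and 13% to 15% at a 30% risk (19.6 to 17.0; 25.2 to 21.4). Because the risks are fixed at the end of the tilt, the percentage does not depend on T. At a 30% symptom-stop risk, T = 10 gives 8.4 to 7.1 and T = 45 gives 37.8 to 32.2.

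**Step 3: a true gain with more high-pressure stops.** Baseline: symptom-stop risk 60%, high-pressure risk 5%, T = 30. Suppose that stimulation halves h1. Counting symptom stops only, the mean rises from 19.6 to 24.1 minutes, a gain of 4.5. All-cause duration starts at 19.2:

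| High-pressure risk under stimulation | Share of stimulated tilts ended by high pressure | All-cause mean | Apparent gain |
|---|---|---|---|
| 5% (unchanged) | 4% | 23.5 min | 4.3 |
| 15% | 12% | 22.4 | 3.2 |
| 30% | 24% | 20.5 | 1.3 |
| 40% | 33% | 19.2 | 0.0 |

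The share is h2/(h1+h2) x (1-exp(-(h1+h2)T)), with the halved h1. For the last row, h1 = 0.01527 and h2 = 0.01703, so 0.527 x 0.6205 = 0.33. Gains are differences of the rounded means.

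**Step 4: a heavier case, symptom hazard unchanged.** With h1 = 0.02 per minute and T = 30, the mean is 22.6 minutes without high-pressure stops. With h2 = 0.01, 0.02 and 0.04 per minute it is 19.8, 17.5 and 13.9. By the same share formula, about 20%, 35% and 56% of all tilts would then end for high pressure. Nothing in the protocol supports rates of that order, so this shows direction only.

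**The case against.** The strongest reply is that the protocol nowhere says a high-pressure stop counts as intolerance. It says only that duration will be tracked, and an SAP that is not available here could add stop-reason coding and censoring. That is a fair limit. Still, the protocol does fix the outcome as unqualified duration, and followed as written that definition gives the result described. The reason for stopping is also best captured at the test, not reconstructed later.

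Several further points stand:

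- CV-scES is meant to keep systolic pressure normal, the stated aim is to avoid life-threatening dysreflexia, and stimulated tests use parameters chosen beforehand. High-pressure stops may be rare.
- Stimulation during the test is optional, and unstimulated tests are also scheduled. The direct pressor effect does not apply to those.
- Continuous pressure, cuff readings and the 0-10 symptom questionnaire are collected, so many stop reasons could be recovered afterwards.
- A request to lie down may itself be intolerance, so requests cannot all be set aside.

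A reader might infer that the cardiovascular comparisons under hypotheses 1a, 1e and 2b could wrongly show no gain. The protocol does not support that. None of these hypotheses names tilt duration. The same section also analyses one-minute mean pressures, the percentage of systolic beats below 110 mmHg, the percentage at least 10 mmHg below supine, and spectral and baroreflex measures. A reader might also infer that a completed tilt is analysed as an exact tolerance time. The protocol does not say how completed tilts are handled.

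**Conclusion.** The point holds in a limited form. Head-up tilt duration, as defined, mixes orthostatic intolerance with stops for persistent high pressure and symptom-free requests. High-pressure stops push the value the wrong way, and they may do so unequally between stimulated tests and the unstimulated baseline.

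The size of the bias cannot be determined from the protocol. On assumed inputs it runs from about 2% of mean tilt time to complete masking of a real gain. Masking needed a rise in high-pressure stop risk from 5% to 40%; with the risk unchanged at 5%, most of the gain still showed. These figures rest on constant hazards, an assumed 30-minute tilt and assumed stop risks. They show direction and are not an estimate for this trial. The consequence is confined to one of several orthostatic measures, which is not a named primary endpoint.

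**What to change.** Leave the stopping rules as they are and change the recording and the outcome definition:

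1. Record the reason each tilt ends: orthostatic symptoms, persistent high pressure, request, or completion.
2. Define orthostatic tolerance as time from the start of tilt to a stop for orthostatic symptoms. Count a request as an event when the Orthostatic Intolerance Questionnaire shows accompanying symptoms.
3. Treat completed tilts and symptom-free requests as censored.
4. Report high-pressure stops separately as a competing outcome, by stimulation condition. Read the two together, since more high-pressure stops leave fewer tilts in which symptoms can be seen.

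The cost is one extra data field, a short change of wording in III.D.2.b, and a summary slightly less simple than a mean duration.
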